#### **1.2** Secondary Objectives

- 1.2.1 Evaluate performance on HVLT-R delayed recall at 12 months following hippocampal-sparing PCI relative to historical control receiving standard PCI.
- 1.2.2 Evaluate composite cognitive function at 6 and 12 months following hippocampal-sparing PCI relative to a historical control receiving standard PCI
- 1.2.3 Evaluate quality of life following hippocampal-sparing PCI relative to a historical control receiving standard PCI.
- 1.2.4 Determine whether development of brain metastases following hippocampalsparing PCI is higher than expected.
- 1.2.5 Determine whether development of leptomeningeal carcinomatosis following hippocampal sparing PCI is higher than expected
- 1.2.6 Evaluate overall survival following hippocampal sparing PCI.

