#### 2.2.2 Trail Making Test

The Trail Making Test A is designed to evaluate visual motor scanning speed and the Trail Making Test B is designed to evaluate executive function (39,40). These tests require patients to connect circles in numerical (part A) or alternating numerical and alphabetical sequence (part B) within a timed interval of less than 5 minutes for each test. Results are reported as the number of seconds required to complete the task with higher scores reflecting higher degrees of impairment.

	Average	Deficient	Rule of Thumb
Trail A	29 seconds	>78 seconds	Most in 90 seconds
Trail B	75 seconds	>273 seconds	Most in 3 minutes

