#### 8.1.3 Secondary Endpoints

- 8.1.3.1 Cognitive function, specifically memory, at 12 months from PCI as measured by the HVLT-R delayed recall
- 8.1.3.2 A composite cognitive function endpoint using the validated Reliable Change Index (48,49) to include the Controlled Word Association Test (COWAT), the HVLT-R-delayed recall, the HVLT-R-trials 1-3 and Trail Making Tests part A and B (TMT)
- 8.1.3.3 Quality of Life (QOL) as measured using the EORTC Quality of Life Questionnaire (QLQ-C30) and Brain Cancer Module 20 (BN20) at baseline, 6 months, and 12 months
- 8.1.3.4 Development of brain metastases at 2 years following completion of radiation therapy will be coded as a binary variable (yes or no)

8.1.3.5 Development of leptomeningeal carcinomatosis at 2 years following completion of radiation therapy will be coded as a binary variable (yes or no)

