#### 8.4 Statistical Methods of Analysis

The primary objective of this study is to evaluate change in cognitive function as measured by the HVLT-R-delayed recall. We will compare hippocampal-sparing PCI to the historical experience of patients who received standard PCI in RTOG 0212. Each patient will be assessed pre-therapy and post-therapy, with the change at 6 months being the primary endpoint. Patient scores on the HVLT-R delayed recall section are whole numbers, ranging from 0 to 12, with lower scores indicating declining cognitive function. The score itself refers to the number of words a patient can recall from a list of 12 words. Therefore, if a patient initially is able to recall 8 words pre-therapy and is, at 6 months, able to only recall 6 words, their change in score would be 2. The primary endpoint (change score) is the difference between the pre-therapy and post-therapy scores. A change score of zero indicates preserved cognitive function. Change scores from -1 to -12 indicated improved cognitive function and are not expected. Summary statistics of the change scores, such as means, medians, standard deviations, and ranges will be listed separately by treatment (sparing PCI and historical standard PCI groups). We hypothesize that change scores from pre-therapy to 6 months post-therapy is lower among patients receiving hippocampal-sparing PCI compared to the historical PCI group in the RTOG study. We will use the Wilcoxon Signed-Rank test to test the change in HVLT-R scores over six months, relative to the expectation based on the historical information, according to the statistical hypotheses given in the sample size section (Section 8.2.1).

The analysis of the secondary outcome of HVLT-R-delay score change at 12 months will be performed as described above for the primary outcome. In addition, we will examine if there appears to be a trend to increasing change score over time for the treatment groups.

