The Reliable Change Index will measure meaningful change between baseline and 6 and 12 months for HVLT–R, Trail Making Test part A and B, COWAT. The Reliable Change Index is derived from the standard error of measurement (SEM) for each test in the battery. The SEM is calculated from the test–retest reliability (r) and the standard deviation of test scores (SD): SEM=sqrt[SD×(1-r)]. The standard error of the difference (SEdiff) is then calculated as SEdiff =sqrt[ $2\times(SEM)^2$ ]. For each test in the neurocognitve battery, the Reliable Change Index value will be determined *a priori* for that particular test to determine whether a change from baseline is clinically meaningful.

We will compute summary statistics and compare our patients to the historical controls based on tests that are appropriate for the type of data.

[figure not shown]
Quality of Life on our study will be assessed using EORTC Quality of Life questionnaire (QLQ-C30) and the Brain Cancer Module 20 (BN 20) pre-therapy, at 6 months, and at 12 months after therapy. For each module, summary statistics of the scores will be reported for each study time point. Change scores in quality of life from pre-therapy to post-therapy will be calculated and tested via paired t-tests for the hippocampal-sparing PCI treatment group. We may fit mixed-effect models to explore changes in quality of life assessments over time.

We will tabulate development of brain metastases within 0.5 mm of the hippocampus. We will report adverse events based on CTCAE v4.0 by frequency tables. We will test the proportion of patients who develop brain metastases via binomial test. Overall survival will be measured from the start of treatment to death or last followup. For subjects who alive or lost follow up at the end of study, overall survival will be censored at the last follow up date. Overall survival probabilities will be estimated via the Kaplan-Meier method; median survival and 95% confidence interval via Greenwood's formula for variance will be reported.

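### The SEM formula for the Reliable Change Index has SD where SD² belongs; applied as printed, every cut-off is off by a factor of sqrt(SD)

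*Combined protocol and SAP*

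**What the plan says.** Secondary objective 1.2.2 is to "Evaluate composite cognitive function at 6 and 12 months following hippocampal-sparing PCI relative to a historical control receiving standard PCI". Section 8.1.3.2 defines the endpoint as "A composite cognitive function endpoint using the validated Reliable Change Index", covering COWAT, HVLT-R delayed recall, HVLT-R trials 1-3 and Trail Making parts A and B.

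Section 8.4 gives the only derivation. It says: "The SEM is calculated from the test–retest reliability (r) and the standard deviation of test scores (SD"). The formula follows directly: "the standard deviation of test scores (SD): SEM=sqrt[SD×(1-r" (the quote stops just before the closing brackets). SEdiff is then the square root of twice the squared SEM. On the cut-offs themselves, the section says: "For each test in the neurocognitve battery, the Reliable Change Index value will be determined" in advance, to decide whether a change from baseline is clinically meaningful.

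The readable text gives no score SD, reliability, multiplier or numerical cut-off for any test. One figure in Section 8.4, next to this material, could not be seen.

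**The concern.** A standard error of measurement has to be in the units of the test score, because it is compared with a change in that score. With SD a standard deviation, the square root of SD×(1-r) is in square-root units. The expression would be right only if SD were a variance, and the text defines it as a standard deviation. No other section gives the correct form.

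The RCI decides who counts as changed at 6 and 12 months. If cut-offs are computed from the printed formula, stable patients are called changed too often on every test with SD above 1, most of all where SD is large. The components of the composite would then be mis-scaled unequally. The comparison with RTOG 0212 would be biased if the historical data were scored with other cut-offs; the documents do not say which were used.

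**Working it through.** **Inputs from the plan**
- The SEM and SEdiff formulas (Section 8.4).
- HVLT-R delayed recall: "Patient scores on the HVLT-R delayed recall section are whole numbers, ranging from 0 to 12" (Section 8.4).
- Trail Making: "Results are reported as the number of seconds required to complete the task" (Section 2.2.2). Averages are 29 s (A) and 75 s (B); deficient limits are 78 s (A) and 273 s (B).

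The plan states no SEM, SEdiff or cut-off, so there is no figure of its own to reproduce.

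**Exact result (no assumptions)**
- Printed: SEM_p = sqrt[SD×(1-r)]
- Correct: SEM_c = SD×sqrt(1-r) = sqrt[SD²×(1-r)]
- SEdiff = sqrt(2)×SEM in both cases.
- Ratio correct/printed = SD×sqrt(1-r) / sqrt[SD×(1-r)] = sqrt(SD).

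The reliability r cancels, and so does any multiplier applied to SEdiff. The two forms agree only at SD = 1; below 1 the error reverses.

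**Unit check**

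Assume a Trail Making SD of 30 s, which is 0.5 min, and r = 0.7.
- Printed, in seconds: sqrt(2×30×0.3) = 4.2 s.
- Printed, in minutes: sqrt(2×0.5×0.3) = 0.548 min = 32.9 s.
- Correct: 30×sqrt(2×0.3) = 23.2 s either way.

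A cut-off that depends on the unit chosen cannot be right.

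**HVLT-R delayed recall (illustration)**

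The SDs in Section 8.2.1 (2.80, 3.19, about 3) are tied to change scores and do not fix the score SD. I assume a score SD of 2 to 3, equal at both visits, normal measurement error and no practice effect.

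On a continuous scale with one-sided multiplier 1.645, the false-decline rate is 1-Phi(1.645/sqrt(SD)) for any r:
- SD 2: 1-Phi(1.645/1.414) = 12.2%
- SD 2.5: 1-Phi(1.645/1.581) = 14.9%
- SD 3: 1-Phi(1.645/1.732) = 17.1%

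The correct formula gives 5.0%. With a two-sided multiplier of 1.96, the false-change rate is 16.6% (SD 2) to 25.8% (SD 3), again against 5%.

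In whole words I take r = 0.7 (assumption), multiplier 1.645 and a continuity-corrected normal with true SEdiff = SD×sqrt(2(1-r)):

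| SD | Cut-off, correct / printed | Words needed, correct / printed | False decline, correct / printed |
|---|---|---|---|
| 2 | 2.55 / 1.80 | 3 / 2 | 5.3% / 16.6% |
| 2.5 | 3.19 / 2.01 | 4 / 3 | 3.5% / 9.8% |
| 3 | 3.82 / 2.21 | 4 / 3 | 6.6% / 14.1% |

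Rounding to whole words can hide the error. With SD 2 and r = 0.6 the cut-offs are 2.94 and 2.08, so 3 words are needed either way and the rate is 8.1% in both cases.

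**Trail Making (rough illustration)**

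Assume the deficient limit lies 2 to 3 SD above average.
- Part A: 78-29 = 49 s, so SD is 49/3 to 49/2 = 16.3 to 24.5 s and sqrt(SD) is 4.0 to 4.9.
- Part B: 273-75 = 198 s, so SD is 198/3 to 198/2 = 66 to 99 s and sqrt(SD) is 8.1 to 9.9.
- False decline with 1.645: 34% to 37% (A) and 42% to 43% (B), instead of 5%.

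If the limits lie anywhere from 1 to 4 SD above average, the factors are 3.5 to 7.0 (A) and 7.0 to 14.1 (B), and false decline is 32% to 41% (A) and 41% to 45% (B).

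For COWAT and HVLT-R trials 1-3 the documents give no usable figure.

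**The case against.** **The square may have been lost when the PDF was read.** The exponent in the SEdiff formula survived, but that formula was captured as typeset mathematics and the SEM formula as plain text, so one says little about the other. This stands as a caution, and it makes the source file the first thing to check. It does not alter the fact that the formula as it reads is wrong.

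**The harm is conditional.** The plan refers to a validated index with references and sets its values in advance, so a transcription slip is the natural reading and the analyst may well use the right form. That is fair. But the printed formula is the plan's only stated rule, and the readable text has no SD, r, multiplier or cut-off that would expose the slip. Because of the unseen figure, the absence of cut-offs can be claimed only for the readable text.

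**The sizes rest on assumptions.** This also stands in part. Section 2.2.2 does not define deficient in SD units. With normally distributed times, the assumed SDs would imply negative completion times for 4% to 12% of people on part A and 13% to 22% on part B. The Trail Making percentages are therefore orders of magnitude only. The HVLT-R whole-word results vary with r: at SD 2 the cut-offs also coincide at r = 0.85 and 0.9, and at SD 2.5 they coincide at r = 0.9. None of this touches the sqrt(SD) factor, which needs no assumption.

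**Conclusion.** The concern holds. As printed, the SEM formula is wrong by exactly sqrt(SD), and SEdiff and every cut-off proportional to it carry the same factor. Whether any patient is misclassified depends on the printed formula being the plan's true text and on cut-offs being computed from it; neither can be settled from the documents. If both are so, the HVLT-R delayed recall cut-off is 1.41 to 1.73 times too small for a score SD of 2 to 3, and the Trail Making cut-offs are too small by a much larger factor. Bias against the historical controls would further require the two groups to be scored with different cut-offs.

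The reach is limited to the secondary composite. The primary Wilcoxon signed-rank test, the sample size of 100 evaluable and 125 enrolled, and the brain-metastasis stopping rule do not use the RCI. The point should be fixed, but it does not threaten the primary result.

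**What to change.** 1. Check the source file for a superscript lost from the SEM formula.
2. If the formula stands as printed, replace it with SEM = SD×sqrt(1-r). The SEdiff formula is correct and stays.
3. For each of the five measures, state the SD with the sample and visit it comes from, the reliability r, the multiplier, and the resulting cut-off. If the figure that could not be seen already gives these, refer to it.
4. Recompute any cut-off already derived from the printed formula, and apply the same cut-offs to the trial patients and to any historical data they are compared with.

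The cost is one corrected formula and at most five recomputed cut-offs. No new data are needed.

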#### 8.5 Safety Monitoring

We have included a formal statistical stopping rule for monitoring the occurrence of brain metastases. The article describing RTOG 0212 reported that the raw proportion of patients with brain metastases is 22% (29/131) at 1 year for the group getting 2.5 Gy in 10 fractions. We established a monitoring rule that will recommend considering stopping the study if there appears to be high probability that the risk of brain metastasis at 1 year is above 22%. Specifically, if the posterior probability that the risk exceeds 25% of brain metastasis by 1 year after treatment is 75% or greater (3:1 odds), then we will consider stopping the study. In this calculation, the number of patients with brain metastasis at 1 year is a binomial random variable. The prior

distribution for the risk of brain metastasis by 1 year is beta with parameters 29 & 102. Although we can apply the stopping rule calculation after every patient, we may monitor in batches of 10. The stopping rule is illustrated in the figure below.

Safety Monitoring Boundary

#### 9. ADVERSE EVENTS AND RECORDING

#### 9.1 Definition of Adverse Event (AE)

An adverse event is the development of an undesirable medical condition or the deterioration of a pre-existing medical condition during or following an exposure to a treatment, whether or not considered causally related to the treatment. An undesirable medical condition may be symptoms (headache, nausea), signs (tachycardia, enlarged liver), or abnormal results of an investigation (MRI, laboratory finding). In clinical trials, from the time of signing an informed consent, an AE may include an undesirable medical condition, occurring at any time, even if no trial treatment has been administered.

#### 9.2 Radiation Related Adverse Events

All radiation related adverse events will be recorded on the local toxicity case report forms.

#### **10. SERIOUS ADVERSE EVENTS (SAE) AND REPORTING**

#### **10.1** Serious Adverse Event

#### 10.1.1 Definition of Serious Adverse Event

A serious adverse event is an AE occurring at any point during a clinical trial that fulfills one or more of the following criteria:

- Results in death.
- Is immediately life threatening.
- Requires in-patient hospitalization or prolongation of existing hospitalization.
- Is a congenital abnormality or birth defect.
- Unexpected event that cause harm or place person at a greater risk of harm than was previously known or recognized, and which was possibly related to the research. Unexpected means that the event was not described in the consent form or the event exceeded the expected severity.
- Is an important medical event that may jeopardize the patient or may require medical intervention to prevent one of the outcomes listed above.

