#### 5.1.6 Risks of Radiation

Short term toxicities of radiation therapy include fatigue, alopecia, erythema or irritation of the skin, dry skin, headaches, worsening of current symptoms, edema of brain requiring steroids, ear pain or discomfort, damage to the baby if patient is or becomes pregnant, seizures, neurologic deficits depending on tumor location, edema of brain requiring surgery, death. Long term toxicities include memory loss, cataracts, edema of the brain requiring steroids, vision loss, hearing loss, necrosis of brain requiring surgery second tumor or cancer caused by radiation.

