#### 7. MANAGEMENT OF TOXICITY

#### 7.1 Acute Toxicity

Acute morbidity potentially associated with therapy will be monitored and recorded on the Radiation Oncology On-Treatment Evaluation Form for all patients from baseline to 90 days after completion of radiation therapy. Grading will be according to the RTOG Acute Morbidity Scoring Criteria as follows:

Organ	Grade 0	Grade 1	Grade 2	Grade 3	Grade 4
Skin	No change over baseline	Faint erythema, epilation, dry desquamation, or decreased sweating	Tender or bright erythema, patchy moist desquamation, moderate erythema	Confluent, moist desquamation other than skin folds, pitting edema	Ulceration, hemorrhage, necrosis
Eye	No change over baseline	Mild conjunctivitis with or without scleral injection, increased tearing	Moderate conjunctivitis with or without keratitis requiring steroids and/or antibiotics, dry eye requiring artificial tears, iritis with photophobia	Severe keratitis with corneal ulceration, objective decrease in visual acuity or in visual fields, acute glaucoma, panopthalmitis	Loss of vision (unilateral or bilateral)
Ear	No change over baseline	Mild external otitis with erythema, pruritis, secondary to dry desquamation not requiring medication. Audiogram unchanged over baseline.	Moderate external otitis requiring topical medication, serous otitis media, hypoacusis on testing only	Severe external otitis with discharge or moist desquamation, symptomatic hypoacusis, tinnitus, not drug related	Deafness

CNS	No change over baseline	Fully functional status with minor	Neurologic findings present sufficient to	Neurologic findings requiring hospitalization	Serious neurologic impairment which included
		neurologic findings, no medications needed	require home care. Nursing care may be required. Medications including steroids and/or antiseizure agents	for initial management	paralysis, coma, or seizures, despite medications. Hospitalization required

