#### 7.2 Late Toxicity

Late toxicity will be recorded on the Radiation Oncology Follow-up form at each follow-up visit greater than 90 days post completion of radiation therapy. Grading will be according to the RTOG Late Radiation Morbidity Scoring Schema as follows:

Organ	Grade 0	Grade 1	Grade 2	Grade 3	Grade 4	Grade 5
Skin	None	Slight atrophy, pigmentation change, some hair loss	Patchy atrophy, moderate telangiectasia, total hair loss	Marked atrophy, gross telangioectasia	Ulceration	Death directly related to late

Subcutaneous Tissue	None	Slight induration and loss of subcutaneous fat	Moderate fibrosis but asymptomatic. Slight field contracture. <10% linear reduction	Severe induration and loss of subcutaneous tissue. Field contracture >10% linear measurement	Necrosis	radiation effect
Spinal Cord	None	Mild L'Hermitte's syndrome	Severe L'Hermitte's syndrome	Objective neurologic findings at or below cord level treated	Mono-, para-, quadra-plegia	
Brain	None	Mild headache, slight lethargy	Moderate headache, great lethargy	Severe headaches, severe CNS dysfunction (partial loss of power or dyskinesia)	Seizures, paralysis, coma	
Еуе	None	Asymptomatic cataract, minor corneal ulceration of keratitis	Symptomatic cataract, moderate corneal ulceration, minor retinopathy or glaucoma	Severe keratitis, severe, retinopathy or detachment, severe glaucoma	Panopthalmitis, blindness	

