#### 11.2 Data Safety Monitoring

All SAE's and major protocol deviations that occur at Johns Hopkins Hospital will be submitted to the Sidney Kimmel Comprehensive Cancer Center Data Monitoring Committee for review per Institutional guidelines. In addition, the overall study safety and potential activation of the study's early stopping rules will be assessed at the time of every SAE. The Data Safety Monitoring Committee with review this trial for safety annually.

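### The serious-adverse-event definition names no disability outcome, so prompt escalation of a disabling sensory or cognitive harm in a patient who is not admitted rests on judgement

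*Combined protocol and SAP*

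**What the plan says.** Section 10.1.1 lists six alternative criteria for a serious adverse event:

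1. Death.
2. Immediate threat to life.
3. "Requires in-patient hospitalization or prolongation of existing hospitalization".
4. "Is a congenital abnormality or birth defect".
5. An unexpected, possibly related event that causes harm or raises the risk of harm. The section adds: "Unexpected means that the event was not described in the consent form or the event exceeded the expected severity".
6. A catch-all: "Is an important medical event that may jeopardize the patient or may require medical intervention to prevent one of the outcomes listed above".

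Section 5.1.6 names the harms to be expected from cranial irradiation: "Long term toxicities include memory loss, cataracts, edema of the brain requiring steroids, vision loss, hearing loss", among others. The acute table in 7.1 puts deafness (ear) and loss of vision (eye) at Grade 4, its top grade. The late table in 7.2 puts "Panopthalmitis, blindness" at Grade 4 for the eye, the highest grade short of death.

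SAE status decides how fast an event travels. Section 10.2 requires SAEs other than deaths to go to the IRB within 10 working days of the principal investigator learning of them. Section 11.2 sends SAEs to the data monitoring committee and says that "the overall study safety and potential activation of the study's early stopping rules will be assessed at the time of every SAE".

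**The concern.** The trial asks whether sparing the hippocampus reduces cognitive harm from prophylactic cranial irradiation. Lasting sensory or cognitive disability is therefore among the harms that a safety committee would most want to hear of quickly. The criteria in 10.1.1 turn on death, threat to life, admission, birth defect, unexpectedness or judgement. A patient can go blind or deaf, or lose the memory needed to live independently, while remaining an outpatient and in no immediate danger. For that patient the text does not compel the fast route, and two investigators could classify the same event differently. The formal statistical stopping rule in 8.5 covers brain metastases only, so prompt review of a disabling toxicity depends on the SAE route.

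**Working it through.** The plan states no figure on this point and none has to be reproduced. The check applies each criterion in 10.1.1 to one case: a patient who is not admitted and develops Grade 4 blindness or deafness, or incapacitating memory loss.

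| Criterion in 10.1.1 | Met in this case? |
|---|---|
| Death | No |
| Immediate threat to life | No |
| Hospitalisation | No, by construction of the case |
| Birth defect | No |
| Unexpected harm | Depends on the consent form and on severity |
| Important medical event | Possible, by judgement |

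**Unexpected harm.** The test is set against the consent form, not against 5.1.6. The consent form is not in the documents available for review, so whether it describes these harms, and how severely, cannot be checked. If it describes vision, hearing and memory loss, the first part of the test fails and only exceeded severity is left. Section 5.1.6 gives no severity for any of the three, so the protocol supplies no benchmark for that comparison.

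**Important medical event.** This criterion has two limbs. The preventive limb points back to the outcomes listed above it, and disability is not one of them. The jeopardy limb stands alone and could take in such a case, but it is undefined and leaves the decision to the investigator.

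**Does the protocol tie these grades to admission?** In the acute table, the Grade 4 CNS entry says that admission is required. The Grade 4 eye and ear entries say nothing about it. The hospitalisation criterion therefore cannot be assumed to catch them.

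**What the toxicity tables cover.** Deafness appears only in the acute table, because the late table has no ear row. Memory loss appears at no grade of either table. Late brain Grade 4 is seizures, paralysis or coma, and the Grade 3 entry on severe CNS dysfunction gives motor signs as its examples.

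**The two routes compared.**

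| | Classed as an SAE | Not classed as an SAE |
|---|---|---|
| IRB | Within 10 working days (10.2) | No expedited report stated |
| Committee | Event submitted; safety assessed at the time (11.2) | Annual review (11.1, 11.2) |
| Record | Case report form | Case report form if radiation-related (9.2); frequency tables (8.4) |

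The difference is one of speed. Ten working days is two calendar weeks (10 / 5 = 2). An annual review can leave an event waiting for up to about 12 months. The two clocks lead to different bodies, so they show scale and are not a strict difference.

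**The case against.** The strongest reply is that the definition is wider than the hospitalisation criterion and that nothing disappears. Much of this stands.

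- Any one criterion is enough. The jeopardy limb and the exceeded-severity test can each make blindness, deafness or loss of independence an SAE.
- A reader might infer that a harm named in 5.1.6 cannot be unexpected. The documents do not support that, because 10.1.1 refers to the consent form. Section 10.2, on deaths, does mention both the protocol and the consent document, so the difference in wording is visible.
- A reader might infer that these harms need not be reported at all. That fails too. Radiation-related events go on case report forms (9.2), late toxicity is recorded at each follow-up visit beyond 90 days (7.2), toxicity reports are part of the annual review (11.1), and adverse events are tabulated (8.4). Memory is also tested at baseline, 6 and 12 months, since it is the primary endpoint.
- A reader might infer that the protocol grades severe memory loss among its worst toxicities. It does not; it only lists memory loss as a risk.
- A disabling event that is an SAE would not count towards the brain-metastasis boundary in 8.5. What it prompts is the wider look at study safety described in 11.2.
- Section 11.2 refers to institutional guidelines, and 11.1 to a centre-wide monitoring plan. Neither is available, and either could carry a broader definition.

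None of this supplies a criterion that clearly compels the fast route for the case examined. It limits the point to expedited reporting.

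**Conclusion.** The point holds in a limited form. Section 10.1.1 names no disability or incapacity outcome, although the protocol lists memory, vision and hearing loss as risks and grades deafness, acute loss of vision and late blindness at Grade 4. When the patient is not admitted, expedited reporting depends on the jeopardy limb or on the harm going beyond what the consent form led one to expect. Failing both, the event is recorded routinely and reaches the committee at annual review.

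What is at stake is delay, at most about 12 months, and inconsistent classification. It is not loss of the data. The upper bound assumes that both discretionary criteria fail and that no institutional rule fills the gap. The documents do not say how often these harms occur or how often they are managed without admission, so no number of affected patients can be given. The analysis of the primary endpoint is not touched.

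**What to change.** Add one bullet to 10.1.1, above the important-medical-event criterion: *Results in persistent or significant disability or incapacity.* Its position matters. Placed there, disability becomes one of the listed outcomes to which the preventive limb of the catch-all refers, so both criteria are repaired by one line.

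A rule making every Grade 4 event an SAE would be a poor substitute. It would miss memory loss, which has no grade, and late deafness, which has no row in 7.2. It would also bring in late skin ulceration and subcutaneous necrosis, which are not the gap identified here.

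The cost is one line of text and a small number of extra SAE reports. Treatment, sample size and analysis are unchanged.
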